6.0 Reporting

Collection of Safety Information. The study activities do not involve any invasive procedure, and it is not anticipated that serious adverse events or unanticipated problems will occur, including events that would trigger suspension of research. However, in the rare chance such an incident does occur, all serious adverse events and unanticipated problems will be reported according to regulatory and reporting requirements outlined in the VHA Handbook 1058.01 within 5 business days of the incident. The Coordinating Center will complete and submit an Unanticipated, Serious Adverse Event (SAE) Report form or Problem Report for each incident to the VA Human Subjects Boards as per the regulatory requirements at each site and the study protocol.

The project coordinator will be responsible for reporting relevant information to the PI on a weekly basis. Any clinical or data safety concerns will be reported to the PI and responsible VA clinician within 24 hours. If the PI is unavailable, the project coordinator will contact an available Co-Investigator ([name], [name], [name]). The PI will determine whether the event is a) serious or non-serious and b) anticipated or unanticipated. The PI will ensure that any necessary actions are taken immediately to address the current patient situation, and then will decide if the team needs to make any changes in the protocol and/or consent forms to prevent future occurrences or better inform future participants. Any deviation to protocol or safety concerns resulting from the study will be communicated by the project coordinator via the submission of an Unanticipated, Serious Adverse Event (SAE) Report form or Problem Report to the VA IRB as per the VHA regulatory requirements and protocol, within 5 business days of an incident.

Method of Collection of Safety Information. If the study is made aware of any Adverse Events through notification by a study participant, VA Quitline Counselor, or email/contact from a study provider, the project coordinator will be responsible for completing the above safety & regulatory report forms (i.e., SAE forms), which the PI will sign prior to submission. Adverse Events will be reported to the VA Human Subject Review Board using the appropriate Central IRB forms.

Frequency of Safety Data Collection. Oversight of project activities and data by the PI will begin immediately. Collection of CDW data will begin as soon as IRB approval is obtained. Twice-weekly lists of potential subjects will be continued until target recruitment goals are met.

Any event that adversely affects participant safety will be recorded as soon as possible after it occurs and be reported within 24 hours to the PI.

Notification of Subjects of Findings Affecting Health and Welfare. This study does not involve any invasive procedure, and it is not anticipated that any findings identified by the study (e.g. survey results) will require notification.

7.0 Privacy and Confidentiality

PHI. Protected Health Information and personal identifying information will be obtained from existing sources (Corporate Data Warehouse, CAPRI/JLV) and from patient subjects. Names, social security numbers, birthdates, ages, appointment dates, treatment dates, date of CT screenings, telephone numbers, and patient addresses will be obtained. Limited screening data will be entered into an electronic subject tracking database that will be maintained on secure servers at the COIN at VA Puget Sound. The tracking database will be used to log subject recruitment and completion of surveys. The tracking database will include subject name, SSN, address, phone number, date they were offered lung cancer screening by their VA provider, and date of receipt of lung cancer screening. The tracking database will also serve as the crosswalk between the subject name and the study ID sequentially assigned by project staff. Data collected as part of this study (subject responses to surveys) will include a study ID with no other patient identifiers, and will be stored separately from the tracking/ crosswalk data.

Data security. Data collection, storage and management for this research project will adhere to all applicable VA policies, the VA Puget Sound Health Care System's Automated Information Systems Security Policy, and the established Data Security Policy of the Seattle/Denver COIN. All electronic study data – including protected health information and de-identified analysis files – will be stored in secure, password protected folders and/or SQL databases on the Seattle HSR&D network. Access will be restricted to the study team. Protected health information will not be disclosed, copied, transmitted by email, or transmitted in total or in part to anyone not connected with the approved protocol and not approved by the VA (via a Data Use Agreement, if necessary) to access the identifiers.

All electronic study data will be in secured and stored in electronic files on the COIN's secure servers at VA Puget Sound. Files will be secured behind the VA firewall with strong password protection restrictions in accordance with VA policy. Access to study files will be restricted to study staff only. The data collected in this study will be used solely for the purpose described in the study protocol.

At no time will copies of data will be placed on laptops, computer desktops, hard drives, portable media, or any other form of media or hardware. Screening data for potential subjects identified in Corporate Data Warehouse data repository will be transferred and stored in electronic format to the VA Informatics and Computing Infrastructure (VINCI) server using secure server-to-server, password-protected media/ technology. Data Use Agreements between project staff and repositories will be executed prior to all data access. The historical and screening CDW data will remain within our designated VINCI workspace environment, which will be restricted to approved project staff only. The VINCI workspace will be accessed remotely from workstations located within COIN offices at VA Puget Sound.

Hardcopies of all study data (such as survey responses) will be kept in locked file cabinets in COIN offices. CDs containing participation records obtained from VA Quitline will also be stored in locked file cabinets in COIN offices, and will be labeled only with a coded study ID (no patient identifiers).

The PIs, co-investigators, and project coordinator will be responsible for monitoring data and study activities. Any deviation from the data security or privacy rules will be immediately reported to the Database Administrator, Privacy Officer and Information Security Officer. Study investigators will access data to identify prospective patients offered lung cancer screening on an ongoing (approximately weekly) basis. The project team will hold regular, biweekly meetings to provide updates and review analyses. Additional, ad hoc meetings will be scheduled to discuss specific findings or challenges.

Upon completion of the research project, the PI in conjunction with the VA Information Security Officer (ISO), and in accordance with VA policy, will ensure that, study data containing sensitive, confidential information will be sanitized and removed from all servers, desktops, removable storage devices, etc. in accordance with Records Control Schedule 10-1. When any study personnel are no longer a part of the research team, the PI will remove that person's access to all study data and notify the VA Information Security Officer of such action. COIN Information Technology personnel will be responsible for maintaining COIN servers where study data will be kept, and will move, backup and remove study data from servers and control access to data stored on COIN servers. All study team personnel with access to sensitive patient data will stay current on their VA approved information security training and VA approved privacy policy training.

8.0 Communication Plan

Each site (NY Harbor and Providence) will submit and obtain R&D approvals. We anticipate NY Harbor and Providence R&D committees will provide guidance about requirements for annual review and/or submitting presentations/manuscripts prior to publication.

The project manager at the Coordinating Center in Seattle will be the point of contact for ensuring that any changes to the protocol or any Serious Adverse Events or Unanticipated Problems will be promptly will be responsible for managing local R&D paperwork and assisting with IRB paperwork.

[name] assumes primary responsibility for oversight of study logistics; formative evaluation, fielding and analyzing survey data; conduct of qualitative interviews; synthesis of formative evaluation findings into feedback reports. [name] will provide oversight of the Project Manager. [name] will assume responsibility for ensuring the study meets overall project deadlines and adheres to the proposed timeline; communication with study team members and participants about study events and results; and timely reporting of study findings internally to operational stakeholders, VA researchers and the scientific community.

PROACT Statistical Analysis Plan (SAP)

Project Title: Promoting Smoking Cessation in Lung Cancer Screening Through Proactive Treatment (PROACT)

Date: February 16, 2023

Project Team: [name], [name], [name], [name], [name], [name]

Contents

1. Study Summary and Aims	2
2. Data Sources	3
3. Study Population.....	3
4. Study Time Period	Error! Bookmark not defined.
5. Sampling and Randomization	3
6. Study Outcome Measures.....	4
7. Study Covariates	5
8. Statistical Analyses and Description of Main Tables.....	6
9. Handling of Missing Data	9
10. Project Links	9
11. Shell Tables and Figures.....	Error! Bookmark not defined.

1. Study Summary and Aims

Study purpose:

Investigate an intervention designed to help Veterans stop smoking.

Study design:

Parallel two-arm cluster randomized clinical trial.

Primary Aim: Conduct a pragmatic randomized trial among smokers participating in lung cancer screening comparing proactive smoking cessation care with unstructured care. We will assess the differences between the two care approaches on 7-day smoking abstinence 12 months after receipt of screening. Assignment of providers to the two care arms will continue until the study is on track to have 540 patients responding (270 responders per arm) to the 12-month survey. Based on our preliminary findings in a pilot study of proactive care, and related trials in other populations of smokers, we hypothesize that smoking abstinence 12 months after screening will be twice as high (18%) in the proactive group compared to expected abstinence rates in the unstructured group (9%).

2. Data Sources

Data Source	Time Period	Description	Analytic variables of Interest
CDW	Data Collection	Electronic health record for Dept. Of Veteran Affairs	Smoking status and patient characteristics
Surveys	Data Collection	Surveys conducted at 3 and 12 months post LCS	Smoking status, quit attempts, and other patient reported outcomes

3. Study Population

Veterans who smoke being screened for lung cancer at the VA Providence or VA New York Harbor.

Inclusion Criteria	Exclusion Criteria

• Current smoker• Participant in lung cancer screening	
• Patients with urgent findings requiring biopsy/immediate attention on the screening CT• Patients with a prior diagnosis of lung cancer or who are receiving active therapy for any cancer other than skin cancer• Patients previously diagnosed with cognitive impairment, dementia, or severe behavioral disorders• Patients who have an indication in chart review of difficulty communicating or participating in telephone counseling sessions

4. Sampling and Randomization

This is a cluster randomized two-arm parallel group trial. Randomization occurred at the provider-level. Lists of providers referring patients to lung cancer screening at Study Site A & Study Site B were

prepared. Providers at each site were pair-matched on patient volume and then randomized to either the intervention arm or the control arm. Randomization was performed using random numbers generated with the R programming language.

Following randomization, all patients of enrolled providers who attended lung cancer screening and met eligibility criteria were considered enrolled in the study, with treatment arm corresponding to the randomized treatment arm of their provider.

5. Study Outcome Measures

					Assessment Timepoint
Measure (Units)	Comments	Data Type	BL	3M ¹	12M
Primary Outcome (1)					
Self-reported smoking cessation at 12 months	Constructed from 12-month survey and EMR data	Binary			✓
Secondary Outcomes (3)					
Experience with Telephone Counseling	Survey only	Binary		✓	
Self-efficacy to quit	Survey only	Likert scale (0-10)		✓	✓
Motivational Assessment	Survey only	Likert scale (0-10)		✓	✓
Perception of susceptibility to harm	Survey only	Summary Score		✓	

6. Study Covariates

			Assessment Timepoint		
Measure (Units)	Comments	Data Type	BL	3M ¹	12M ¹
Treatment Assignment	Intervention or Control	Binary	✓		
Covariates for primary and secondary models (2)					
Site		Binary			
Additional covariates for primary and secondary sensitivity models (4)					
Additional variables collected²					
Gender	Self-report from screening and baseline questionnaires	Binary	✓		
Marital/partner status	Self-report from screening and baseline questionnaires	Categorical	✓		
Age	Self-report from screening and baseline questionnaires	Continuous	✓		
Highest level of education	Self-report from screening and baseline questionnaires	Ordinal	✓		
Current employment status	Self-report from screening and baseline questionnaires	Categorical	✓		
Service connection	EHR	Binary	✓		
¹ Months post-LCS					

		Assessment Timepoint			
Measure (Units)	Comments	Data Type	BL	3M ¹	12M ¹

7. Statistical Analyses and Description of Main Tables

Aim 1 statistical analyses

The primary analysis will be an intent-to-treat based comparison of the two intervention arms. The analysis will be performed at the level of the individual. Clustering of patients within providers will be accounted for in the analysis by the inclusion of a random intercept for provider. The primary analysis will be based on the following random intercept logistic regression model

$$\text{logit}^{-1} \left(P(Y_{ij} | Treatment, Site) \right) = \beta_0 + \alpha_j + \beta_1 Treatment + \beta_2 Site$$

Where Y_{ij} is an indicator variable for whether the i^{th} patient of the j^{th} provider had quit smoking at 12 months, *Treatment* is a binary indicator for assigned treatment arm, and *Site* is a binary indicator for VA medical center (New York Harbor or Providence). The α_j represent random intercepts for each provider and are assumed to follow a common $N(0, \sigma^2)$ distribution. We will report point estimates and 95% confidence intervals for the odds ratio $\exp(\beta_1)$. Confidence intervals will be computed using bootstrap methods. A test of the null hypothesis of no association ($\beta_1 = 0$) will be performed using a likelihood ratio test. A p-value of less than 0.05 will be taken as sufficient evidence to reject the null hypothesis of no association.

Analyses for secondary outcomes will use models with similar predictor terms but with different link functions depending on the outcome. The table below describes model types in more detail for each outcome.

Analysis	Description	Outcome	Independent Variable(s)	Model type	Statistical Test
Primary outcome	Smoking cessation at 12 months	Indicator of smoking abstinence at 12 months	Binary treatment indicator; Binary site indicator; Categorical provider	Logistic regression with random intercept for provider	

Analysis	Description	Outcome	Independent Variable(s)	Model type	Statistical Test
			(clustering variable)		
Secondary outcome	Use of smoking cessation support within 3 months of LCS	Indicator for receipt of medication or behavioral counseling	Binary treatment indicator; Binary site indicator; Categorical provider (clustering variable)	Logistic regression with random intercept for provider	
Secondary outcome	Use of smoking cessation support within 12 months of LCS	Indicator for receipt of medication or behavioral counseling	Binary treatment indicator; Binary site indicator; Categorical provider (clustering variable)	Logistic regression with random intercept for provider	
Secondary outcome	Smoked in the last 7 days (3 month survey)	Indicator for smoking	Binary treatment indicator; Binary site indicator; Categorical provider (clustering variable)	Logistic regression with random intercept for provider	
Secondary outcome	Smoked in the last 7 days (12 month survey)	Indicator for smoking	Binary treatment indicator; Binary site indicator; Categorical provider (clustering variable)	Logistic regression with random intercept for provider	
Secondary outcome	Quit attempts since LCS (3 months)				
Secondary outcome	Tried to reduce or cutdown	Indicator for Yes	Binary treatment indicator;	Logistic regression with	

Analysis	Description	Outcome	Independent Variable(s)	Model type	Statistical Test
	since LCS (3 months		Binary site indicator; Categorical provider (clustering variable)	random intercept for provider	
Secondary outcome	Quit attempts since LCS (12 months)				
Secondary outcome	Tried to reduce or cutdown since LCS (12 months	Indicator for Yes	Binary treatment indicator; Binary site indicator; Categorical provider (clustering variable)	Logistic regression with random intercept for provider	
Secondary outcome	Support Satisfaction	Ordered categorical (A little/not at all satisfied, somewhat satisfied, very satisfied)	Binary treatment indicator; Binary site indicator; Categorical provider (clustering variable)	Ordered logistic regression with random intercept for provider	
Secondary outcome	Motivation to quit	Score on motivation to quit scale	Binary treatment indicator; Binary site indicator; Categorical provider (clustering variable)	Linear regression with random intercept for provider	
Secondary outcome	Self-efficacy for quitting	Score on self-efficacy scale	Binary treatment indicator; Binary site indicator; Categorical provider	Linear regression with random intercept for provider	

Analysis	Description	Outcome	Independent Variable(s)	Model type	Statistical Test
			(clustering variable)		
Secondary outcome	Perceived susceptibility to lung cancer	Score on susceptibility scale	Binary treatment indicator; Binary site indicator; Categorical provider (clustering variable)	Linear regression with random intercept for provider	

8. Handling of Missing Data

In descriptive statistics, we will describe the extent of missing data. We will examine whether there is differential missingness in outcomes across treatment arms and sites. We will assess the extent to which the distributions of patient characteristics differ between those with the primary outcome and those without the primary outcome.

Patients may have missing data due to survey non-response or missing EHR data. The primary analysis will be a complete-case analysis among those who have a smoking status at 12 months. In sensitivity analyses, we will adapt a method to examine the impact of non-ignorable missingness on the study's primary conclusions. We will use the following model, which incorporates a Missing Not at Random (MNAR) missingness mechanism through a sensitivity parameter representing the odds ratio of smoking cessation between people with missing outcomes and people without missing outcomes.

$$\text{logit}^{-1}(P(\text{Smoking})) = \beta_0 + \beta_1 \text{Tx} + \beta_2 \text{Site} + \beta_3 \text{Missing}$$

9. Project Links

Clinical Trials Website:

<https://clinicaltrials.gov/ct2/show/NCT03612804>

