5.6 Data Analysis

Sample size determination. Our target sample size of 270 respondents per arm with complete 12-month outcome information was selected to have sufficient (80%) power to detect a doubling of abstinence rates (Relative Risk = 2) using a multilevel random effects model with patients clustered by randomized provider. The assumed intraclass correlation coefficient for the provider clustering effect is assumed to be 0.01. Power is based on a two-sided test with type-1 alpha error rate of 0.05%. Due to randomization, we do not anticipate needing to adjust for patient covariates.

Intent-to-treat (ITT) analysis We will utilize an intent-to-treat approach and include all participants who meet study eligibility criteria and are assigned to a study arm, regardless of whether they participated in all of the care components of that arm (e.g. declined proactive telephone counseling). Our primary analysis will focus on participants for whom we have complete 12-month abstinence (target n=270 per arm).

Missing outcome data. For secondary analyses, we will examine outcomes for all eligible screening patients who are current smokers offered screening by a participating randomized provider during the study period. This analysis will include patients who do not participate in the survey assessment of cessation outcomes. We will perform two secondary analyses. The first will assume that patients who do not participate in the survey assessment (e.g. missing abstinence outcomes) will be considered continued smokers, which is a typical intent-to-treat approach for cessation trials. We do not anticipate differential missing data across study arms. Second, we will address potential missing cessation data by requesting a HIPAA waiver and waiver of informed consent to review EMR data for all eligible patients to estimate an administrative assessment of cessation, based on HealthFactors data and whether patients report quitting at a subsequent visit or when they return for annual lung cancer screening. The methods developed by McGinnis et al, will be used to construct this administrative cessation variable.

(Note, due to COVID pandemic changes in lung cancer screening utilization and study enrollment timelines, the missing data protocol using EMR data was adapted for the primary outcome. See the Statistical Analysis Plan.)

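### Providers were pair-matched on patient volume, but the primary model adjusts only for site; adding one volume term is a free, small improvement

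*SAP*

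**What the plan says.** SAP section 4 describes the randomization: "Providers at each site were pair-matched on patient volume and then randomized to either the intervention arm or the control arm". The design factors are therefore site and, within site, patient volume.

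The primary model in SAP section 7 (Aim 1) contains treatment, site and a random intercept: "Clustering of patients within providers will be accounted for in the analysis by the inclusion of a random intercept for provider". The matching row of the analysis table lists the same three terms. Neither has a term for volume, panel size or pair. The same structure passes to the other endpoints: "Analyses for secondary outcomes will use models with similar predictor terms but with different link functions depending on the outcome".

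Protocol 5.6 comments on adjustment once: "Due to randomization, we do not anticipate needing to adjust for patient covariates". That covers patient characteristics, not a provider-level randomization factor.

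Protocol 5.1 describes the balancing differently. Providers are randomized in blocks on panel size, which is taken as a proxy for past screening volume, and newly hired providers are randomized as they arrive.

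**The concern.** When a factor is used to restrict randomization, the usual practice is to carry it into the model. If the factor predicts outcome, matching makes the arms more alike than simple randomization would, so the true variance of the treatment contrast falls. A model without the factor leaves that share in the provider variance, so its standard error is somewhat too large. The cost is a slightly conservative test and a little lost power.

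The plan follows this practice for site but not for volume, and does not say why. What is at stake is consistency between design and analysis, and at most a small amount of power.

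**Working it through.** **Inputs from the documents.** Abstinence 9% versus 18% and 270 completers per arm (Protocol 5.6, SAP section 1). About 300 providers (Protocol 5.2), so 540/300 = 1.8 completers per provider. Between-provider correlation: "The assumed intraclass correlation coefficient for the provider clustering effect is assumed to be 0.01". Two-sided alpha 0.05 (SAP section 7; Protocol 5.6 prints 0.05%, read here as 0.05).

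**Assumptions not in the documents.** The coefficient of variation (CV) of cluster size, taken from 0 to 2, and R², the share of between-provider variance that volume explains. Protocol 5.3 says annual orders per provider run from one or two to hundreds, so a large CV is plausible, but no figure is given.

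**The plan's own power figure.** With 270 per arm and no clustering, the pooled two-proportion formula gives 86.6%. The design effect 1 + (1.8 − 1) × 0.01 = 1.008 lowers this to 86.4%. The stated 80% is therefore conservative on these inputs.

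**Effect of the omitted term under matching.**

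- Effective cluster size: m = 1.8 × (1 + CV²).
- Variance factor the unadjusted model estimates: D0 = 1 + (m − 1) × 0.01.
- True variance factor after matching, also the factor the adjusted model estimates: D1 = 1 + (m − 1) × 0.01 × (1 − R²).
- Null standard error: s0 = √(2 × 0.135 × 0.865/270) = 0.02941.
- Alternative standard error: s1 = √((0.09 × 0.91 + 0.18 × 0.82)/270) = 0.02915.
- Power without the term: Φ[(0.09 − 1.96 s0 √D0)/(s1 √D1)].
- Power with the term: Φ[(0.09 − 1.96 s0 √D1)/(s1 √D1)].
- Type I error without the term: 2[1 − Φ(1.96 √(D0/D1))].

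Example, CV 2 and R² = 1: m = 9, D0 = 1.08, D1 = 1.00. Without the term, (0.09 − 0.0599)/0.02915 = 1.032, so power is 0.849. With it, (0.09 − 0.0576)/0.02915 = 1.110, so power is 0.866. The gain is 1.7 points. Type I error without the term is 0.042.

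| CV | Gain, R² = 0 | Gain, R² = 0.25 | Gain, R² = 1 | Power without term, R² = 1 |
|---|---|---|---|---|
| 0 | 0 | 0.0 | 0.2 | 0.865 |
| 1 | 0 | 0.1 | 0.6 | 0.861 |
| 1.5 | 0 | 0.3 | 1.0 | 0.856 |
| 1.8 | 0 | 0.4 | 1.4 | 0.852 |
| 2 | 0 | 0.4 | 1.7 | 0.849 |

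Gains are in percentage points.

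**Simulation.** The SAP model with its likelihood ratio test was simulated with providers paired on volume within site, ICC 0.01, realised CV about 1.84 and 3,000 replicates per setting. Power without and with log volume:

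- Volume unrelated to quitting: 0.850 and 0.850.
- Explains a quarter: 0.844 and 0.846 (gain 0.2, SE 0.25).
- Explains all, log-linear: 0.831 and 0.851 (gain 1.9, SE 0.4). With 15% late entrants handled by an indicator, the gain is again 1.9.
- Explains all, as a step at the top third of providers: 0.847 and 0.849 (gain 0.3, SE 0.3).
- Explains all, U-shaped: 0.836 and 0.836 (gain 0.0, SE 0.2).

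Simulated type I error was 0.045 without the term and 0.050 with it. A separate simulation at CV 2 with volume explaining everything log-linearly gave 0.836 and 0.855, again a gain of 1.9 points (SE 0.4).

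**Analysed sample size.** The primary outcome is "Constructed from 12-month survey and EMR data", so the number analysed may not be 540. At CV 2 and R² = 1 the matched-design gain is 1.8 points with 400 patients (73.4% to 75.2%) and 1.4 points with 700.

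**The case against.** The strongest case against is that nothing turns on this. No passage says volume predicts quitting; Protocol 5.1 gives balance between arms as the purpose. The random intercept already allows for provider differences. Of the volume effects simulated, only the log-linear, explains-all case gives a gain distinguishable from zero. A single slope does not represent pairs, and the step and U-shaped results show that it can miss a volume effect. All of this stands, and it limits the size of the point. It does not give a reason to leave out a factor that was used to randomize, when including it costs one or two degrees of freedom.

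The covariate table in SAP section 6 cannot settle the matter. Its headings announce more covariates than can be read, and rows may have been lost. A volume term in a sensitivity model therefore cannot be ruled out. The point rests on the primary model formula and its table row, which agree with each other.

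Two stronger readings are tempting.

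- A reader might infer that ignoring the matching makes the primary test invalid. It does not: the error runs towards conservatism.
- A reader might compare ordinary design effects with and without the volume share and obtain 2.7 points at CV 2 (0.840 to 0.866). That comparison ignores that matching has already removed the volume share from the true variance. Allowing for this gives 1.7.

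**Conclusion.** The omission is real and of the lowest severity. The planned analysis is unbiased and does not inflate type I error. If volume predicts quitting, it is slightly conservative (about 0.042 by formula at CV 2 when volume explains all between-provider variance).

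At ICC 0.01, 300 providers, 540 patients and CV up to 2, the power gain is zero if volume is unrelated to quitting, under about 0.5 points if it explains a quarter of between-provider variance, and at most about 2 points if it explains all of it log-linearly. CV and the share explained are assumptions. An ICC above the planned 0.01, far fewer providers or a larger CV would raise the ceiling, but the plan assumes none of these.

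A reader might also infer that the trial is underpowered without the term. At 540 patients, power exceeds 80% with and without it in every setting within this range.

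**What to change.** 1. Reconcile Protocol 5.1 (blocks on panel size) with SAP section 4 (pairs on patient volume), and state which factor was used.
2. Add one fixed, pre-randomization term for that factor to the SAP section 7 primary model, for example log volume, and list it in SAP section 6 among the primary and secondary model covariates. It then reaches the secondary models through their similar predictor terms. The term approximates the matching factor rather than reproducing the pairs; fixed pair effects would need about 300/2 = 150 parameters for 540 patients.
3. For providers randomized later without that value, set the covariate to a constant and add a late-entry indicator. Do not put a different measure into the same slope.
4. If outcomes by arm have already been examined, report the adjusted model as a labelled sensitivity analysis. The SAP is dated February 2023 and describes enrolment in the past tense ("all patients of enrolled providers who attended lung cancer screening and met eligibility criteria were considered enrolled in the study"), but the documents do not settle whether this has happened.

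The cost is SAP wording and one degree of freedom, or two with the indicator. Protocol 5.1 already has screening volume reviewed from the Corporate Data Warehouse for providers with past orders, so no new data collection is needed for them.
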